3.3.6.1 Aortic wave reflection assessment

“Using applanation tonometry at the level of left radial pulse, arterial waveforms will be recorded during 8-second with a high-fidelity SPC-301 micromanometer (Millar Instrument©, Texas, USA) by means of a fully automated and validated system (SphygmoCor, Atcor Medical), version 9.0 software (AtCor Medical©, New South Wales, Australia). Three minutes before aortic wave reflection assessments, manual blood pressure measurements (Mercury sphygmomanometer, WelchAllyn©, New York, USA) will be performed according to guidelines²⁹ in order to calibrate radial pulse wave. Aortic pressure waveforms will be derived from the peripheral radial pressure waves using a validated generalized transfer function. This has been shown to accurately estimate aortic pressure waveforms based on the assumption that mean blood pressure does not change along the arterial tree. In case of decreased aortic compliance or increased peripheral resistance, the reflected wave come back faster to the aorta. This can be assessed by the augmentation index (Alx; 100× augmentation pressure/pulse pressure), representing the pressure boost induced by the return of these reflected waves to the aorta, expressed as a percentage of the pulse pressure. Higher values of Alx indicate an earlier return of the reflected wave to the aorta. Ventricular ejection time determines the aortic pressure waveform. In case of heart rate alterations with ventricular

ejection time modifications, Alx changes may be masked or overestimated. This is why all the Alx presented in the article will be corrected for heart rate (Aix75) according to the linear relationship established by Wilkinson et al,³⁷ namely, that for every 10-bpm increase in heart rythm, Alx decreases by 4%. These measurements will be made ten minutes before and three times after exposure. “*Clinical and Experimental Pharmacology and Physiology* (2009) **36**, 784–789

3.3.6.2 Pulse wave velocity measurements

“We will assess the carotid-femoral pulse wave velocity (PWV) using a sequential waveform measurements approach at carotid and femoral sites with applanation tonometry (SPC-301 micromanometer) and SphygmoCor software as previously described.²⁹ The pulse waves time period between the carotid and femoral sites will be assessed with an electrocardiograph-derived R wave as a fixed point. This pulse wave time will be the average of 10 consecutive beats. The difference between the path in cm from the left carotid sampling site to the suprasternal notch, and the path in cm from the left femoral sampling site to the suprasternal notch will be used to define the distance which the pulse wave travels.” *Clinical and Experimental Pharmacology and Physiology* (2009) **36**, 784–789

3.3.7 exhaled breath condensate

The participant will close his nose with a nose-clip and approach the mouthpiece. For collecting breathing condensate, the participants will breathe via an elbow piece with connected mouthpiece through a nonrebreathing valve block in which inspiratory and expiratory are separated. During expiration, the breathing air flows through a lamellar condenser which is cooled by the refrigerator circuit. This lamellar condenser is cooled down to -30°C. In this condenser, the breathing condensate is precipitated on the inner wall and drops in the sample collection vessel. The machine which will be used is a ECoScreen

(VIASYS Healthcare GmbH, Hoechberg, Germany). The exhaled breath condensates will be drawn at the start of the experimental and 90 minutes after exposure.

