A. In comparison to pursuit of PG/GLY vaping with or without nicotine, e-cigarette cessation for five days:

- Increases transcutaneous O₂ tension and O₂-haemoglobin saturation
- Decreases respiratory rhythm
- Increases lung diffusing capacities and forced expiratory flows
- Increases maximal rate of oxygen consumption during cycle ergospirometer test
- Modifies heart rate variability
- Decreases arterial stiffness
- Decreases serum PG/GLY and nicotine concentrations

B. In comparison to PG/GLY vaping with nicotine, e-cigarette cessation for five days or PG/GLY vaping:

- Increase cutaneous vascular conductance and decrease arterial stiffness
- Increase acetylcholine and heat mediated vasodilation

C. Each of the three experimental sessions (e-cigarette cessation, PG/GLY vaping and pursuit regular consumptions):

- Induces specific serum, urine and exhaled breath condensate metabolomics profiles
- Induces specific serum proteomics profile

This research proposal tests also the following hypothesis regarding acute effects of PG/GLY vaping with and without nicotine in regular e-cigarettes users:

A. In comparison to baseline, PG/GLY vaping without nicotine:

- Decreases transcutaneous O₂ tension and O₂-haemoglobin saturation
- Increases respiratory rhythm
- Increases serum PG/GLY concentrations
- Induces specific serum, urine and exhaled breath condensate metabolomics profiles

B. In comparison to baseline and PG/GLY without nicotine, PG/GLY vaping with nicotine:

- Decreases transcutaneous O₂ tension and O₂-haemoglobin saturation
- Decrease continuous vascular conductance and increase arterial stiffness
- Increases respiratory rhythm
- Increases serum PG/GLY and nicotine concentrations
- Induces specific serum, urine and exhaled breath condensate metabolomics profiles

3. Methodology

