3.3.4.1 Skin continuous vascular conductance

Skin continuous microcirculatory blood flow will be assessed using a PeriFlow system 5000, PF 5010/5020 with the thermostatic probe 457 (Perimed®, Järfälla, Sweden) at the level of the right arm at least 5 cm from the PF 5040 with combined transcutaneous O₂ and CO₂ - E5280 electrode; and mean arterial pressure will be measured throughout the sessions with a beat-to-beat hemodynamic monitoring system (Finometer Pro, FMS®, Amsterdam, the Netherlands) on the right middle finger.¹⁷ Cutaneous vascular conductance will be then calculated as skin continuous microcirculatory blood flow divided by mean arterial pressure.

3.3.4.2 Evaluation of microvascular reactivity to pharmacological stimulation.

"Endothelium-dependent and -independent vasodilatation of the skin microcirculation (measured in perfusion units, PU= 10 mV) will be noninvasively and continuously evaluated by laser Doppler fluxmetry technique in combination with iontophoresis (Periflux 5001 and Perilont, Perimed, Jarfalla, Sweden) of acetylcholine (ACh), after vaping or sham vaping and iontophoresis of sodium nitroprusside (SNP), minutes after vaping or sham vaping. The laser Doppler flowmetry probes will be constantly heated at throughout the study so as to avoid changes in microvascular blood flow due to local skin temperature variations. Drug-delivery

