electrodes (PF 383, Perimed) incorporated into the head of the laser probe (PF 481-1, Perimed), will be carefully placed, by the use of specific double sided skin adhesive patches on the forearms. The drug-delivery electrodes will be filled with 200 μ l ACh dissolved in distilled water and will be attached with the laser probe to a standardized site on the right forearm (anterior and proximal part) that had no visible veins. The dispersive electrode will be attached approximately 15 cm away from the electrophoresis chamber, according to the manufacturer's instructions. A protocol of three fixed doses (current intensity-delivery time) will be employed, resulting in an incremental dose \pm response curve. After measuring the resting flow, three doses of 0.1 ACh dissolved in distilled water will be delivered using a cathodal current (0.1 mA for 80 seconds, with total charges of 8 millicoulombs) at 120-second intervals. The mean values of the resting flow will be considered to be the basal flow values for each patient. Using a new delivery electrode applied on the left forearm, three doses of a solution of SNP dissolved in distilled water will be delivered using an anodal current (0.1 mA for 80 seconds, with total charges of 8 millicoulombs at 120-second intervals). The curves of the microvascular flow increases induced by SNP and Ach will always have a total recording time of 20 minutes: three times 80-second of iontophoresis at 120-second intervals and 10 minutes to reach the plateau response after the last dose. ¹⁸ (CLINICS 2011;66(4):599-605)

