3.3.4.3 Heat test

“Using another laser probe (PF 457, Perimed) at the level of right distal arm (anterior side) that will be positioned at the beginning of the recordings. Maximal skin microvascular vasodilatation will be measured after vaping or sham vaping using prolonged (20 minutes) local heating of the laser probe to 44°C. The use of the area under the blood flow/time curve (AUC) for assessing skin microvascular reactivity using Laser Doppler Perfusion Monitoring is well validated because it represents the global flow response to different physiological and pharmacological stimuli.”³³⁻³⁵ (CLINICS 2011;66(4):599-605)

3.3.5 fractional exhaled carbon dioxide

Fractional exhaled carbon monoxide will be assessed at the start of each experimental session using a Smokerlyzer (SineFuma©, Breda, Holland). Fractional exhaled carbon monoxide should be less than 5 ppm.³⁶

3.3.6 arterial stiffness indices

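### Heat, acetylcholine and nitroprusside responses are stated as raw flow and pulse wave velocity has no pressure term; if arterial pressure differs between sessions, impaired dilation could be masked and a pressure effect read as stiffness

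*Combined protocol and SAP*

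**What the plan says.** Two vascular measures carry a haemodynamic correction:

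- Resting skin flow (3.3.4.1): "Cutaneous vascular conductance will be then calculated as skin continuous microcirculatory blood flow divided by mean arterial pressure".
- Augmentation index (3.3.6.1): all values "presented in the article will be corrected for heart rate", because a change in heart rate could otherwise hide or exaggerate a change in the index.

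The remaining measures have none stated:

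- Acetylcholine and nitroprusside (3.3.4.2): vasodilatation is "measured in perfusion units, PU= 10 mV", and the output is a flow curve: "The curves of the microvascular flow increases induced by SNP and Ach will always have a total recording time of 20 minutes". Mean resting flow is taken as each participant's basal value, but the section does not say whether the response is a ratio to it, a difference from it or an absolute level.
- Heat test (3.3.4.3): "The use of the area under the blood flow/time curve (AUC) for assessing skin microvascular reactivity" is cited as validated. The curve is of flow, and no division by pressure or by a baseline is given.
- PWV (3.3.6.2): a path length and an ECG-referenced transit time. "This pulse wave time will be the average of 10 consecutive beats". Pressure does not enter.

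The data for a correction are already collected (3.3.4.1): "mean arterial pressure will be measured throughout the sessions with a beat-to-beat hemodynamic monitoring system". The document has no statistical analysis section, so no covariate model supplies the missing term elsewhere.

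The outcomes matter to Goal B in Section 2. It predicts that cessation or nicotine-free vaping, compared with nicotine vaping, will "Increase cutaneous vascular conductance and decrease arterial stiffness", and will also increase dilation to acetylcholine and heat.

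**The concern.** Flow through a skin bed depends on how dilated the bed is and on the pressure driving it. The plan recognises this for resting flow but not for the stimulated responses, which use the same laser Doppler technique. PWV has a parallel problem: it rises passively as distending pressure rises, with no change in the arterial wall. Section 3.3.6.1 itself says that augmentation index responds to peripheral resistance as well as to aortic compliance. A claim about wall stiffness therefore leans on PWV.

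If MAP is higher in the nicotine session, the two omissions pull in opposite directions within one hypothesis. Raw flow would be inflated for a given dilation, which works against detecting the impairment that Goal B predicts. PWV would be inflated without wall change, which works in favour of the stiffness prediction. The crossover removes stable differences in pressure between people, but not a pressure difference that the session itself produces.

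**Working it through.** **The plan's own figure.** The only calculated figure is the sample size in 3.3.13, which concerns transcutaneous oxygen pressure. With a difference of 10 mm Hg, SD 7 mm Hg, two-sided alpha 0.05 and 80% power, the two-group normal approximation gives 2 × (7 × (1.960 + 0.842) / 10)² = 7.7, so 8 per group and 16 in total. It reproduces, and nothing below depends on it.

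**Inputs**

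- From 3.3.4.1: conductance = flow / MAP, hence flow = conductance × MAP.
- From 3.3.4.2 and 3.3.4.3: the stimulated responses are in flow units.
- From 3.3.6.2: PWV has no pressure term.
- Assumed, because the documents give no blood pressure effect of nicotine: MAP ratio r (nicotine over comparator) of 1.05 to 1.10, with 1.03 and 1.15 as wider limits.
- Assumed, because the documents give no pressure dependence of PWV: PWV proportional to MAP to the power e, with e from 0.25 to 1.

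**Formulas.** If raw flow is equal in two sessions, conductance in the session with higher pressure is 1/r of the other, so the hidden fall is 1 − 1/r. The PWV rise from pressure alone is r^e − 1.

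| Assumed MAP rise | Conductance fall hidden | PWV rise, e = 0.25 | e = 0.5 | e = 1 |
|---|---|---|---|---|
| 3% | 2.9% | 0.7% | 1.5% | 3.0% |
| 5% | 4.8% | 1.2% | 2.5% | 5.0% |
| 10% | 9.1% | 2.4% | 4.9% | 10.0% |
| 15% | 13.0% | 3.6% | 7.2% | 15.0% |

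**Masking of a real effect.** Suppose conductance truly falls by 10%.

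- With MAP up 10%, raw flow is 0.90 × 1.10 = 0.99 of its comparator value, so the fall almost disappears.
- With MAP up 5%, it is 0.90 × 1.05 = 0.945, so about half of the fall shows.

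**When the iontophoresis distortion cancels.** Let C0 and C1 be basal and stimulated conductance, with the same MAP at both moments.

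- Ratio to basal flow: (C1 × MAP) / (C0 × MAP) = C1 / C0. MAP cancels.
- Increment over basal flow: (C1 − C0) × MAP. MAP does not cancel.
- Absolute level: C1 × MAP. MAP does not cancel.

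The plan does not say which form is used. The ratio is not neutral either: it depends on C0, and Goal B predicts that cutaneous conductance differs between the nicotine session and the others.

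**The case against.** Several points on the other side stand.

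- **Silence is not a decision.** The 3.3 subsections describe measurement, and no endpoint has a stated analysis model. A reader might infer that the sponsor has chosen to interpret PWV and flow uncorrected, so that a false result will follow. The documents support only that this could happen.
- **The pressure difference is not documented.** Section 1.3 mentions nicotine-induced vasoconstriction as an explanation for transcutaneous hypoxia with tobacco smoking. It gives no MAP effect, and Section 2 has no blood pressure hypothesis. If MAP does not differ, the correction leaves the comparison essentially unchanged.
- **Part of the microvascular distortion may cancel.** It would largely do so if iontophoresis responses were ratios to basal flow. For the heat AUC no baseline is stated.
- **Nitroprusside is a partial check.** A general pressure artefact should appear there too. The check is incomplete, because nitroprusside is given on the other forearm and possibly at another time. Even so, it would go too far to conclude that neither the flow nor the PWV result can be read as a vessel property.
- **Scope.** A reader might extend the flow problem to acute hypothesis B. That hypothesis lists vascular conductance, already divided by MAP, and arterial stiffness. It does not list acetylcholine or heat responses, so only the stiffness part is exposed there.
- **MAP is measured after exposure.** It may lie on the path from nicotine to PWV. Resting every stiffness claim on the adjusted difference alone would replace the total effect with a pressure-independent one, and with 16 to 21 participants that estimate will be less precise. This is a good reason to report both.

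None of this explains why resting flow is divided by MAP and stimulated flow is not.

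**Conclusion.** The point holds in a conditional form. The omission is plain on the page: the heat, acetylcholine and nitroprusside responses are stated as flow, PWV has no pressure term, and the pressure signal needed for both is recorded. Whether bias follows depends on whether MAP differs between the nicotine session and the other two, which is plausible but not quantified in the documents.

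Under an assumed MAP rise of 5% to 10%, raw flow hides a conductance fall of about 5% to 9%. This follows directly from the plan's own formula. For iontophoresis it applies to absolute levels or increments and not to a ratio to basal flow. The corresponding PWV rise of about 1% to 10% also rests on the assumed elasticity of 0.25 to 1 and is less certain. A lower MAP with nicotine would reverse both directions.

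These are secondary outcomes. The primary comparison of transcutaneous oxygen pressure and the sample size are untouched.

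**What to change.** - **3.3.4.2 and 3.3.4.3:** express resting, heat, acetylcholine and nitroprusside responses as conductance, that is, perfusion units divided by the finger MAP recorded at the same moment, as 3.3.4.1 already does. Take the AUC of conductance. State whether the iontophoresis response is an absolute level, an increment or a ratio to basal.
- **3.3.6.2:** pre-specify the between-session PWV difference in two forms: unadjusted, as the total effect, and adjusted for MAP at each PWV reading. Describe a difference as pressure-independent wall stiffness only if it persists after adjustment. State that MAP may mediate the nicotine effect, and that with 16 to 21 participants the loss of a difference after adjustment does not show that the wall is unchanged.

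Fix both choices before the data are examined, so that the metric cannot follow the result.

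The cost is a few sentences and some processing time. No device, visit or sample is added, because beat-to-beat pressure is already recorded throughout (3.3.1 and 3.3.4.1). The downside is a second PWV estimate that is less precise and may be less favourable to the stiffness hypothesis.

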3.3.8 Urine and venous blood samples

Blood will be drawn in the left antecubital vein before and 60 minutes after exposure. Urine specimens will be collected one hour before and 100 minutes after exposure.

3.3.9 Lung function and diffusing capacity evaluation

“In order to detect lung diffusing perturbations at a pulmonary capillary or membrane level induced by vaping, we will assess effects of e-cigarettes cessation on lung diffusing capacities for carbon monoxide (DLCO) and nitric oxide (DLNO) measured with a double nitric oxide/carbon monoxide single breath technique at the Laboratory of Exercise Physiology (ULB – Faculty of Motor Sciences – Pr. [name]). Briefly, the transit of carbon monoxide through the alveolocapillary membrane and into the plasma and intraerythrocytic compartments determines the DLCO, as defined by the Roughton and Forster equation. On the other hand, the DLNO is thought to represent the true membrane diffusing capacity because of its very high affinity for hemoglobin and its independence from pulmonary capillary blood volume. Therefore, the DLNO/DLCO ratio can be used to differentiate thickened alveolocapillary membranes (both DLNO and DLCO are decreased, and the DLNO/DLCO ratio is normal) and decreased perfusion of ventilated alveoli (the DLNO less decreased than the DLCO; therefore, the DLNO/DLCO ratio is elevated).”²⁰ (*J Appl Physiol* (1985) 2014;116:919-26.)

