3.3 Project plan and various step

The 5h-sessions will take place in the morning at the Hôpital Erasme. During each session, participants will be tested before and after acute exposure at the Cardiology Laboratory (ULB – Pr. [name]) for: 1) noninvasive continuous hemodynamic parameters (Electrocardiogram monitoring (AdInstrument[®]) and a beat-to-beat hemodynamic monitoring system¹⁷ Finapres Medical Systems[®]) 2) continuous respiratory rhythm, end-tidal carbon dioxide and blood oxygen saturation (Capnostream[®]);²⁸ 3) transcutaneous oxygen and carbon dioxide partial pressures (Perimed[®]);¹⁰ 4) skin microcirculatory blood flow by means of laser Doppler perfusion monitoring (continuous vascular conductance, heat test, acetylcholine and sodium nipride iontophoresis) (Perimed[®]);¹⁸ 5) Fractional exhaled carbon monoxide will be assessed at the start of each experimental session using a Smokerlyzer (SineFuma[®], Breda, Holland); 6) arterial stiffness indices (Sphygmocor[®]);²⁹ 7) exhaled breath condensate (Viasys Ecoscreen[®]);¹⁹ 8) Urine and 9) venous blood sample. Then, the participants will be directed to the Laboratory of Exercise Physiology, Faculty of Motor Sciences (ULB – Pr. [name]) to perform assessment of: 10) lung function tests plus capillary and membranous lung diffusing capacity as well as maximal ergometer cycle test²⁰ (details in appendix) (figure 2). After completion of clinical study in all participants, biological samples will undergo proteomics²¹ (ULB – Pr. [name]) and metabolomics²² (UMons – Pr. [name]) analysis (details in appendix).

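### Section 3.3.9 says a thickened membrane leaves the DLNO/DLCO ratio normal, but by its own premises the ratio falls, so an isolated membrane effect fits neither arm of the rule

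*Combined protocol and SAP*

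**What the plan says.** Section 3.3.9 measures DLCO and DLNO together to find out whether vaping disturbs gas transfer at the capillary or at the membrane level. It sets out two premises:

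- For carbon monoxide, "the transit of carbon monoxide through the alveolocapillary membrane and into the plasma and intraerythrocytic compartments determines the DLCO". The section rests this on a named model, with the words "as defined by the Roughton and Forster equation".
- For nitric oxide, "the DLNO is thought to represent the true membrane diffusing capacity because of its very high affinity for hemoglobin". The second reason it gives is "its independence from pulmonary capillary blood volume".

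From these it draws a rule with two arms:

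- Thickened membrane: "both DLNO and DLCO are decreased, and the DLNO/DLCO ratio is normal".
- Reduced perfusion of ventilated alveoli: "the DLNO less decreased than the DLCO; therefore, the DLNO/DLCO ratio is elevated".

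It gives no numeric normal range for the ratio, no threshold, and no rule for reading a change in the ratio between sessions. Section 3.3 lists "lung function tests plus capillary and membranous lung diffusing capacity as well as maximal ergometer cycle test" among the assessments. Hypothesis A in section 2 expects diffusing capacities to rise after five days without vaping and does not mention the ratio.

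**The concern.** The first arm does not follow from the premises. If DLNO tracks the membrane alone and DLCO also has a blood step, a loss confined to the membrane reduces DLNO by the full fraction and DLCO by less. The ratio then falls.

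What is at stake is the purpose of the section, which is to assign an effect to the membrane or to the capillary bed. A true membrane effect, with a lower ratio while vaping and a higher one after cessation, has no place in the rule. A loss that removes membrane and capillary bed in equal proportion meets every condition of the membrane arm. Section 1.4 names alveolar collapse as part of the working hypothesis. If collapse removes both components about equally (an assumption), it would be reported as membrane thickening.

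**Working it through.** The plan gives no figure on this point, so there is nothing to reproduce. The check is whether the rule follows from the premises.

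**Inputs**

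- From section 3.3.9: DLCO has a membrane step and a blood step in series; DLNO reflects the membrane only and does not depend on capillary volume.
- Standard form of the named equation, which the section does not write out: 1/DLCO = 1/M + 1/B, where M is the membrane component and B the blood (capillary) component.
- Formal version of the DLNO premise: DLNO = k·M, with k constant.
- Assumed, because the documents give no value: x = M/B. The main range is 0.5 to 1.5. The wider range of 0.25 to 4 corresponds to a membrane share of the CO resistance, f = 1/(1 + x), of 0.8 down to 0.2.

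**Formulas**

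- Ratio: DLNO/DLCO = k·M·(1/M + 1/B) = k(1 + x).
- M falls 20%, B fixed: DLNO −20%; DLCO is multiplied by 0.8(1 + x)/(1 + 0.8x); the ratio changes by −0.2x/(1 + x).
- Recovery from that state: the reciprocals of those factors, so DLNO rises by 1/0.8 − 1 = +25%.
- B falls 20%, M fixed: DLNO 0%; DLCO is multiplied by (1 + x)/(1 + 1.25x); the ratio changes by +0.25x/(1 + x).
- Both fall 20%: DLNO −20%, DLCO −20%, ratio 0%.

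Example at x = 1: a 20% membrane loss multiplies DLCO by 1.6/1.8 = 0.889 (−11.1%) and changes the ratio by −0.2/2 = −10%.

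**Results (% change)**

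| M/B | f | M −20%: DLCO | M −20%: ratio | Recovery: DLCO | Recovery: ratio | B −20%: DLCO | B −20%: ratio |
|---|---|---|---|---|---|---|---|
| 0.25 | 0.80 | −16.7 | −4.0 | +20.0 | +4.2 | −4.8 | +5.0 |
| 0.5 | 0.67 | −14.3 | −6.7 | +16.7 | +7.1 | −7.7 | +8.3 |
| 1.0 | 0.50 | −11.1 | −10.0 | +12.5 | +11.1 | −11.1 | +12.5 |
| 1.5 | 0.40 | −9.1 | −12.0 | +10.0 | +13.6 | −13.0 | +15.0 |
| 4.0 | 0.20 | −4.8 | −16.0 | +5.0 | +19.0 | −16.7 | +20.0 |

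**Reading the results**

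1. The perfusion arm follows from the premises: a capillary loss raises the ratio.
2. The membrane arm does not. The ratio falls for every x above zero. It stays the same only if the blood step is negligible (x near 0), which contradicts the first premise and would also remove the perfusion arm, or if M and B fall in the same proportion.
3. The direction does not depend on NO having no blood-side resistance at all. If 10% of the NO resistance lies in the blood, a 20% membrane loss still lowers the ratio, by 14.3% at f = 0.2 and by 2.0% at f = 0.8.
4. The ratio alone cannot separate membrane recovery from a capillary loss of the same size (+11.1% against +12.5% at x = 1). The levels can: in recovery DLNO and DLCO both rise (+25% and +12.5%), whereas in capillary loss DLCO falls (−11.1%) and DLNO does not move.

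**The case against.** A reader might infer that membrane recovery after cessation would be reported as reduced perfusion, because both raise the ratio. The documents do not support that. The perfusion arm is more than a raised ratio: it also requires DLCO to be decreased, with DLNO decreased less. Recovery raises both. The misreading would arise only if the between-session change in the ratio were read without the levels, which the plan neither specifies nor excludes.

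Other points on the plan's side:

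- **The text is a rationale, presented as quoted from a cited source.** This is so, and no test or endpoint is built on the ratio. It is nevertheless the only guidance the plan gives for reading DLNO and DLCO together, and quoting it does not reconcile the conclusion with the premises beside it.
- **Normal is not the same as unchanged.** This stands in part. With no range defined, a small fall could still count as normal: a 20% loss at f = 0.8 gives −4%, and a 10% loss gives −2%. At the lower membrane shares the fall is 10% or more.
- **The membrane and capillary components are already to be assessed.** Section 3.3 lists them and points to an appendix for details. No separate appendix is in the text reviewed, so a component analysis may be described there. That would make the fix cheaper but would not correct the rule.
- **Capillary volume may not stay fixed when the membrane thickens.** True, and an equal change in both does leave the ratio unchanged. But the rule presents a normal ratio as the mark of the membrane state, as opposed to the perfusion state, and under the premises it marks a mixed one.

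**Conclusion.** The membrane arm of the ratio rule in section 3.3.9 is wrong as written, judged against that section's own premises. At fixed capillary volume, a 20% membrane loss lowers the ratio by about 7% to 12% for M/B of 0.5 to 1.5, and by 4% to 16% over the wider assumed range. An isolated membrane effect matches neither arm, and an equal loss of both components would carry the membrane label.

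The direction rests on the series form of the named equation and on DLNO being proportional to the membrane component. The size rests on M/B, which the documents do not give. The weight is limited: the point affects the mechanistic reading of a non-primary outcome. The primary objective (transcutaneous oxygen, section 3.3.13), the sample size and the hypothesis that diffusing capacities rise are unaffected.

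**What to change.** - **Correct the rule in section 3.3.9.** State that, under the stated premises, the ratio falls with an isolated membrane loss, rises with an isolated capillary loss, and is unchanged when both fall in equal proportion. Add the pattern expected on recovery: for the membrane, DLNO, DLCO and the ratio all rise.
- **Name the analysis behind the mechanistic conclusion.** Compare the membrane and capillary components between sessions within participant. In the notation above, M = DLNO/k and 1/B = 1/DLCO − k/DLNO, so k should be fixed in advance and used for every session. Alternatively, compare DLNO, DLCO and the ratio between sessions and interpret the three together, never the ratio alone.

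The cost is a few sentences and a calculation on measurements already planned. Settling it before the data are analysed avoids choosing the mechanism after seeing the results.
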